## **3.6     *Recruitment & Compensation***

Patients will be mainly recruited from [name] ALS Clinic or will have called our center to inquire about the study. Since [name] clinic and our phone lines are open to all relevant demographic groups, all groups will have access to this study. In addition we will post the following on the Duke ALS Clinic website and Twitter feed: "Duke ALS Curcumin Study is now open. Call name at telephone # for details." No compensation will be provided.

## **3.7     *Consent Process***

Consent will be obtained by [name], or by his study coordinator over video/telephone services. Potential participants will be given all the time they need to review the written consent and ask questions about it. No study procedures will occur prior to the consent form being signed.

### **3.8 Capacity to Give Consent**

Only potential participants with appropriate capacity to provide informed consent will be offered a consent form.

### **3.9 Risk Assessment**

Curcumin appears reasonably safe. Large meta-analyses indicate that participants have not been recorded to have had a major adverse event. Side effects are infrequent (<10%) mostly gastrointestinal such as nausea, constipation, diarrhea, indigestion, and abdominal pain. Some participants also experienced hot flashes (26-28). This side effect profile is fairly similar to that experienced by a small American pilot trial utilizing Theracurmin in patients with mild cognitive impairment (19).

Risk associated with participation in the Duke or PLM database include loss of confidentiality. Risks of logging into Internet for any website including PLM include inadvertently downloading malicious software such as viruses that could put personal information or computer integrity at risk. These risks are minimized by the properties of the PLM website (see below).

Participants will be provided with contact numbers for the research staff. All sites will have an appropriate staff member available 24 hours a day, 7 days a week in the event of an emergency. Participation in this research study is purely for research purposes, and is not intended to provide any direct benefit to the volunteers other than altruism (knowledge that they are helping investigators develop better treatments, and potentially helping other patients down the road). No at risk populations such as minors, prisoners, pregnant women, or cognitively impaired adults will be included in this study. Patients who elect not to participate will have standard of care options for their ALS including participation in [name] multi-disciplinary ALS clinic and the drug riluzole.

### **3.10 Costs to Subjects**

There is no cost to subjects for participating in this study.

## **4 DATA ANALYSIS & STATISTICAL CONSIDERATIONS**

### **4.1.1 *Historical Controls***

For each enrolled participant, three matched historical controls will be identified from the PatientsLikeMe database. Participants will be matched according to their ALSFRS-R progression rate before they start on the Theracurmin (estimated by assuming their score was normal at 48 on the date of symptom onset). Full details of the matching process are described in a previous paper (7).

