### 2.3 Success of Previous Hybrid Virtual/Remote Trial

We previously conducted an open-label, single-center, hybrid-virtual 12-month trial of Lunasin for patients with ALS (6). This single-center trial featured broad inclusion criteria, historical controls, mostly virtual data collection, and real-time results. Participants measured their ALSFRS-R score, weight and perceived efficacy, and recorded these monthly on PatientsLikeMe (PLM; an online platform described section 2.7). ALSFRS-R decline was compared to historical controls. For each enrolled participant, PLM identified 3 historical controls matched according to pre-treatment ALSFRS-R progression, as in their previous Lithium study (7). We had 90% power to detect 50% slowing in decline of ALSFRS-R scores.

Although there were no significant differences in ALSFRS-R ( $p=0.99$ ) between study participants and historical controls, the study's outcomes suggested that there is utility and internal validity in a virtual trial model. Enrollment rate was 9.1 participants per site per month, which is the fastest rate of any ALS trial in history. As in most ALS trials, our 50 participants were primarily white (94%) males (58%), mean age of 60, limb onset disease (82%), taking riluzole (60%). However, our participants had longer disease duration than those in most trials, and several had non-invasive ventilation, PEG and/or tracheostomy, which are traditional exclusion criteria. This trial population was therefore more representative of the population seen in ALS clinics. In spite of enrolling patients with longer and more advanced disease, the survivor retention rate was 84%, while the survivor retention rate in traditional ALS trials is 78% (5).

We also looked at the accuracy of patient recorded ALSFRS-R and weight measurements. Lin's concordance (C) showed high agreement between coordinator and participant derived ALSFRS-R and weight respectively at month 1 ( $C=0.9939, 0.9947$ ) and month 12 visits ( $C=0.9428, 0.9905$ ). These results suggest that participant recorded ALSFRS-R scores and weight are sufficiently accurate to be used in a clinical trial.

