## **3.3 *Outcome Measures***

### **3.3.1 *ALSFRS-R***

The ALSFRS-R will be determined at all video/telephone visits (Appendix D). ALSFRS-R is a quickly administered (five minute) ordinal rating scale (ratings 0-4) used to determine patients' assessments of their capability and independence in 12 functional activities. All 12 activities are relevant in ALS. Initial validity was established in ALS patients by documenting change in ALSFRS-R scores correlated with change in strength over time, and it was closely associated with quality of life measures and predicted survival (23). The test-retest reliability is greater than

0.88 for all 13 items. The ALSFRS-R declines linearly with time over a wide range during the course of ALS. Recent work has shown that the measure can be conducted over the phone (24), and it can even be reliably conducted and recorded online by patients themselves (25). The ALSFRS-R will be administered to participants over video/telephone by the study coordinator at Duke on their enrollment visit. During this visit, the coordinator will also teach participants how to complete this measure themselves and to use the EM interface to record it. Calls from the coordinator will be made at weeks 1, 2 and 3 to provide additional training. Starting at week 4, participants will be asked to fill out the ALSFRS-R test on their PLM profile once every 30 days.

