### 3.5.1 Inclusion Criteria

Each primary participant must meet all of the following criteria at screening and baseline (unless otherwise specified) to participate in the study:

1. Male or female, aged at least 18 years.
2. Sporadic or familial ALS diagnosed as possible, laboratory-supported probable, probable, or definite as defined by revised El Escorial criteria.
3. Patient is able to understand and express informed consent (in the opinion of the site investigator).
4. Patient has access to the Internet on a desktop computer, laptop, or tablet and has a working email address.
5. Patient or caregiver is willing and able to use a computer and enter data on a secure website.
6. Patient is able to read and write English.
7. Patient is expected to survive for the duration of the trial.
8. Women must not be pregnant (will have evidence of a negative pregnancy test obtained by local physician within past 7 days or be post-menopausal)
9. Women must not be able to become pregnant (e.g., post-menopausal, surgically sterile, or using adequate birth control methods) for the duration of the study and three months after study completion. Adequate contraception includes: abstinence, hormonal contraception (oral

contraception, implanted contraception, injected contraception or other hormonal contraception, for example patch or contraceptive ring), intrauterine device (IUD) in place for  $\geq 3$  months, barrier method in conjunction with spermicide, or another adequate method.

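### Section 4.1.1 states matching on average slope since onset only, so a difference in disease stage between participants and controls would pass uncorrected into the unadjusted primary t-test, in a direction the documents do not settle

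*Combined protocol and SAP*

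**What the plan says.** Section 4.1.1 takes three historical controls per participant from the PatientsLikeMe database. Participants are to be "matched according to their ALSFRS-R progression rate before they start on the Theracurmin", and that rate is "estimated by assuming their score was normal at 48 on the date of symptom onset". No other matching variable is named; full details are left to a cited paper (reference 7). Section 2.3 describes the predecessor trial in the same terms: "PLM identified 3 historical controls matched according to pre-treatment ALSFRS-R progression".

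Section 4.1.2 compares progression rates by a one-tailed t-test at 5% and mentions no covariates.

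Sections 3.5.1 and 3.5.2 set no limit on ALSFRS-R score, disease duration or ventilatory support. The criterion closest to stage is "Patient is expected to survive for the duration of the trial", repeated as a life-expectancy exclusion. On the earlier trial, section 2.3 reports that "our participants had longer disease duration than those in most trials, and several had non-invasive ventilation, PEG and/or tracheostomy".

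On the scale itself, section 3.3.1 says: "The ALSFRS-R declines linearly with time over a wide range during the course of ALS".

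**The concern.** The matching variable is a ratio. It fixes how many points were lost per month on average since onset, but not where on the scale the patient now stands or how long the disease has lasted. If decline were linear over the whole scale, that would not matter. The protocol does not claim this, and entry is open to patients at any score. Two patients with the same average slope can then have different expected declines over the next 6 months without any drug effect.

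A t-test without covariates has no means of removing such a difference. At stake is the primary comparison of an open-label study with no concurrent ALS control group for function: a stage imbalance could be read as a treatment effect, or could hide one.

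**Working it through.** The plan gives no figure for stage balance, so there is none to reproduce on that point. The one related figure, the mean rate in 4.1.2, checks: 11 points / 12 months = 0.92, stated as about 0.9 per month.

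**1. What the match fixes.** Slope = (48 − S)/D, with S the current score and D the months since onset.
- At 1.0 per month: (48 − 38)/10 = 1.0 and (48 − 8)/40 = 1.0.
- At 0.9 per month: (48 − 39)/10, (48 − 30)/20, (48 − 10)/42.2 and (48 − 3)/50 all equal 0.9.

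All patients on one line are equally good matches under the stated rule.

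**2. Where the floor acts.** At 0.9 per month the expected 6-month loss is 0.9 × 6 = 5.4 points. A patient at 3 can lose at most 3, and one at 1 at most 1, so at the mean rate the hard floor acts only at scores of about 5 or less. The patient at 8 in step 1 would lose 6 × 1.0 = 6 points and has 8 to lose. Above about 5, any effect of stage requires the curve to flatten, which is an assumption.

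**3. Size, on assumed inputs.** Suppose a share x of participants declines at a fraction f of the matched rate and controls are unaffected. Apparent slowing is x(1 − f):
- x = 10%, f = 0.5: 5%
- x = 20%, f = 0.5: 10%
- x = 20%, f = 0: 20%

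The documents give neither x nor f. The figures are on the high side, because they give flat participants the average rate. Slope cannot exceed 48/D, so at an assumed 120 months it is at most 48/120 = 0.4. If 20% of participants are completely flat at that rate and the rest match at 0.9, apparent slowing is (0.2 × 0.4)/(0.2 × 0.4 + 0.8 × 0.9) = 0.08/0.80 = 10%, not 20%.

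**4. Effect on the test with no drug effect.** Inputs: 6-month decline 11/2 = 5.5 points; completers 50 × 0.85 = 42.5; controls either 42.5 (the 1:1 comparison in 4.1.2 with equal loss) or 150 (three per participant in 4.1.1). The 6-month SD is not given; 4 to 8 is assumed, around the stated 12-month SD of about 8. Error = Φ(Δ/SE − 1.645), with SE = SD × √(1/n₁ + 1/n₂). For example, with SD 4 and 42.5 v 42.5, SE = 4 × √(2/42.5) = 0.868; 0.55/0.868 = 0.634; Φ(−1.011) = 0.156.

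| Apparent slowing | Δ, points in 6 months | Error, 42.5 v 42.5 | Error, 42.5 v 150 |
|---|---|---|---|
| 5% | 0.275 | 7–9% | 7–11% |
| 10% | 0.55 | 9–16% | 11–20% |
| 20% | 1.10 | 16–35% | 20–48% |

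The low end of each range is SD 8, the high end SD 4. A shift of the same size the other way would take the error below 5% and make a true 2.75-point difference (half of 5.5) look like 2.75 − 0.55 = 2.20.

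**5. Direction.** A simulation without drug effect (assumed S-shaped score curve, 50 participants, three controls each, pool of 3,000) shows how the sign depends on the stage mix. Slope-only matching gave about 24–55% apparent slowing when participants were later-stage than the pool, about 0% when stages were equal, and 19–50% apparent worsening when participants were earlier-stage. Matching on slope and score brought the results to between about −6% and +9%. The curve and stage mixes are assumed, so this supports the sign and the remedy, not a size for this trial.

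**The case against.** The strongest reply is that 4.1.1 is a summary. The cited paper may match on further variables, and the documents cannot exclude that. This stands. It limits the point to the rule as stated, and it is itself a reason to write the variables into 4.1.1, since the primary comparison depends on them.

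A reader might infer that the design favours the drug, because late-stage participants are set against earlier-stage controls. The documents do not support this. No restriction on stage is stated for controls either, and the PatientsLikeMe pool's stage mix is not given. The longer duration reported in section 2.3 is relative to other trials, not to PatientsLikeMe members.

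A reader might also infer that the survival criterion selects stable participants. Being expected to live 6 months is not a condition on the rate of functional decline.

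Finally, the predecessor used matching described in the same way, in a longer-duration population, and reported p=0.99. That gives no sign of a large bias toward slowing. It does not exclude a modest one, and it does not show that the present cohort will have the same stage mix.

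**Conclusion.** The concern holds in a limited form. As stated, matching fixes average slope but not stage, entry does not restrict stage, and the primary test adjusts for nothing, so any stage imbalance between participants and controls would go uncorrected. Its existence, direction and size cannot be read from the documents.

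The 5–20% range rests on assumed shares and rates and on unaffected controls. It is an illustration, well short of the 50% sought. It still matters, because the test rejects on significance and not on reaching 50%: at 10% apparent slowing the nominal 5% error becomes 9–20% over the assumed SDs and both control counts. Imbalance the other way would mask benefit. Reading this as a demonstrated bias toward efficacy would go beyond the documents. As the remedy is cheap, the change should be made.

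**What to change.** - **4.1.1:** Name every matching variable in the protocol. Keep the pre-treatment slope match and add current ALSFRS-R score at the index date as a second variable where enough controls exist. Slope and score together determine duration, since D = (48 − S)/slope.
- **4.1.2:** Replace the unadjusted t-test with a regression of progression rate on group, adjusted for baseline ALSFRS-R and months since onset.
- **Reporting:** Give baseline score and duration for both groups. Add a sensitivity analysis that leaves out near-floor participants with their controls, using a threshold fixed in advance.

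The slope match should not be replaced by calipers on score and duration. With illustrative calipers of 3 points and 3 months, the patient at 38 after 10 months could be paired with slopes from (48 − 41)/13 = 0.54 to (48 − 35)/7 = 1.86, around a true 1.0.

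The cost is protocol wording, a modified database query, a little more analysis work and slightly looser slope matches for some patients. Score and onset date are already needed to compute the slope, so no new data are required from participants.

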### **4.1.2 *Primary Hypothesis and Sample Size***

For the primary hypothesis, we will run a t-test comparing the ALSFRS-R progression rate in our participants to a group of matched historical controls identified from the PatientsLikeMe community. This type of analysis has previously been used to look for treatment effects in

patients with ALS taking lithium (7), dexpramipexole and various forms of sodium chlorite (29) and lunasin (6). We made the following assumptions to calculate a sample size requirement for this analysis:

1. The mean ALS-FRS progression in 12 months is 11 points (rate of ~0.9 points/month) and the standard deviation at 12 months is ~8 ALS-FRS points (estimates based on unpublished data from PatientsLikeMe.)
2. The effect size we are looking for is to halve the mean progression rate
3. The treatment is not having a harmful effect (allows us to use a one-tailed comparison)
4. There is a 5% chance of seeing an effect this big by chance alone
5. We desire a 90% chance of finding an effect this big, assuming it is real
6. There will be a dropout rate of 15% over 6 months. We had a 16% survivor drop-out rate over 12 months in our prior Lunasin trial (6).

Based on these assumptions we will again need to enroll 50 participants (and compare them to 50 matched historical controls).

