### **3.3.6 Retention**

Retention will be assessed by looking at the dropout rate at 6 months (the percentage of surviving enrolled patients who complete the Month 6 Visit). A previous meta-analysis of traditional clinical trials showed the mean ALS participant dropout rate to be 22% at 12 months (5). Our previous virtual trial with Lunasin had a dropout rate of 16% at 12 months (6).

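### The plan gives both 150 and 50 as the number of matched controls, and its primary t-test neither adjusts for the matching variable nor defines the on-study rate

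*Combined protocol and SAP*

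**What the plan says.** On the controls, section 4.1.1 says "For each enrolled participant, three matched historical controls will be identified from the PatientsLikeMe database". It names the matching variable: "Participants will be matched according to their ALSFRS-R progression rate before they start on the Theracurmin". That pre-treatment rate is defined, by taking a score of 48 at symptom onset. The cited paper is invoked for the matching process only.

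On the test, section 4.1.2 says "we will run a t-test comparing the ALSFRS-R progression rate in our participants to a group of matched historical controls". No paired form, matched-set term or covariate is given. The sources cited there are earlier uses of this type of analysis. The same section ends by saying that the trial will enroll 50 participants and "compare them to 50 matched historical controls".

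On the data, section 3.3.1 says "Starting at week 4, participants will be asked to fill out the ALSFRS-R test on their PLM profile once every 30 days". Scores are also taken at enrollment and at weeks 1 to 3. In those first weeks section 3.4.2 has the coordinator's score compared with the participant's, and differences reconciled as part of training. Nothing says whether the on-study rate is a fitted slope or a change divided by time. Nor does the plan say which visits enter, what window applies to controls, or how missing scores and deaths are handled.

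On losses, section 4.1.2 assumes "There will be a dropout rate of 15% over 6 months" and adds "We had a 16% survivor drop-out rate over 12 months in our prior Lunasin trial".

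**The concern.** This is the only test of the primary hypothesis, and three of its elements are open or inconsistent.

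- **Number of controls.** 150 and 50 cannot both be right, and the power depends on which is used.
- **Matching variable.** Matching balances the groups on pre-treatment rate. If that rate also predicts on-study rate, a plain group t-test leaves predictable variation in its standard error, although the variable that would remove it is already collected.
- **On-study rate.** Without a rule, the same scores can yield different rates. In an open-label trial with historical controls, the rule could be chosen after the data are seen.

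**Working it through.** **1. The plan's own figure.** Inputs from section 4.1.2: mean decline 11 points and SD about 8 over 12 months, halving (difference 5.5), one-sided 5%, power 90%, dropout 15%. With equal groups, n = 2 × 8² × (1.645 + 1.282)² / 5.5² = 36.2, so 37 per group, and 37/0.85 = 43.5, so 44 enrolled. The stated 50 does not follow from these inputs, but it exceeds what they require.

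**2. 50 or 150 controls.** Three controls for each of 50 participants is 150. After dropout, 50 × 0.85 = 42.5 participants remain (all controls taken as kept). On the rate scale the mean is 11/12 = 0.917 and the SD 8/12 = 0.667 points/month. SE = 0.667 × √(1/42.5 + 1/N controls). Power is from the noncentral t.

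| | 50 controls | 150 controls |
|---|---|---|
| SE, points/month | 0.139 | 0.116 |
| Power, 50% slowing | 94.8% | 98.9% |
| Power, 30% slowing | 62.5% | 76.4% |

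This treats the 12-month SD as shrinking in proportion to time, which gives a 6-month change SD of 4. The plan states no 6-month SD. For a 6-month difference of 5.5/2 = 2.75 points:

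| Assumed 6-month SD | 50 controls | 150 controls |
|---|---|---|
| 4 | 95% | 99% |
| 5.66 (8/√2) | 75% | 87% |
| 8 | 50% | 63% |

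**3. Not adjusting for the matching variable.** Let ρ be the correlation of on-study rates within a matched set. With close matching on pre-treatment rate alone and a linear relation, ρ is about r², where r is the correlation of pre-treatment with on-study rate. The plan gives neither, so ρ = 0.2, 0.3 and 0.5 are assumed (r about 0.45, 0.55, 0.71). For n complete 1:3 sets, the group t-test works with variance SD² × (4/3)/n, while the true variance is SD² × (4/3)(1 − ρ)/n. The SE is therefore too large by a factor 1/√(1 − ρ), and the true one-sided size is P(Z > 1.645 × that factor).

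| ρ | SE factor | True size |
|---|---|---|
| 0 | 1.000 | 5.0% |
| 0.2 | 1.118 | 3.3% |
| 0.3 | 1.195 | 2.5% |
| 0.5 | 1.414 | 1.0% |

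Power at 30% slowing was simulated with 1:3 sets, 15% random dropout, scores at months 0 to 6 and an assumed visit-error SD of 1.5. The three figures are for ρ = 0.2/0.3/0.5, with Monte Carlo error about 2.5 points:

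- group t-test on slopes: 73/74/73%
- slope regressed on group and pre-treatment rate: 80/82/87%
- mixed model: 72/77/85%

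At 50% slowing all of them reach 96% or more, on the proportional SD.

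**4. The undefined on-study rate.** The simulation assumed no drug effect, with 15% of participants lost according to their observed decline (log-odds 1.0 per SD) and all controls kept. None of this is in the plan. False positives are for ρ = 0.2/0.3/0.5 against a nominal 5%.

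| Rate rule | False positives | Bias in mean rate |
|---|---|---|
| Completers, (baseline − month 6)/6 | 13/12/10% | 9% apparent slowing |
| Slope, at least 4 scores | 4/4/2% | under 1% |
| Slope, at least 2 scores | about 1% or less | 11% against Theracurmin |

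A different scaling of the dropout model gave the same directions with other sizes: 11% apparent slowing, about 5%, and 35% against. With weaker dependence (log-odds 0.25) the completer rule gives 6/5/3% false positives and 2% apparent slowing. If controls are lost alike, its bias is 0%.

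**5. Training scores.** A minimum of four scores could be met by enrollment and weeks 1, 2 and 3 alone. With visit-error SD 1.5, the SE of that slope is 1.5/√Σ(t − t̄)². With t at 0, 7, 14 and 21 days expressed in months, this is about 2.9 points/month, against a mean rate of 0.92.

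**The case against.** The best defence is that the t-test does benefit from the matching, since the groups are balanced on pre-treatment rate and only the standard error ignores it. The error is on the safe side, and at the hypothesised 50% slowing the power is ample. More controls than planned can only help. Section 3.4.3 provides reminders and calls for missed entries, and section 2.3 reports monthly compliance of at least 88% through month 6 in the earlier trial. Most of this stands. The claim of ample power is the exception, because it rests on a 6-month SD that the plan does not give.

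A reader might infer three stronger things that the documents do not support:

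- **That ignoring the matching inflates false positives.** It does the reverse.
- **That the trial will be biased by dropout.** The figures in step 4 need a completer rule, progression-related loss and fully retained controls, none of which the plan states.
- **That deaths come on top of the 15%.** Section 3.3.6 defines retention as "the percentage of surviving enrolled patients who complete the Month 6 Visit", and the earlier trial's 16% is labelled a survivor figure. The planning 15% carries no such label, covers half the time, and may already leave room for deaths. Expected survival for the trial is also an entry criterion.

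Nor does the plan call the t-test unpaired. That is the natural reading, because a simple paired test cannot take 1:3 sets without a rule and none is given.

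**Conclusion.** The point holds in a limited form. The conflict between 150 and 50 controls is plain from the text and needs no assumption. On the 12-month inputs it moves power at 50% slowing only from 94.8% to 98.9%. The gap widens, and power may fall below the planned 90%, if the 6-month SD is relatively larger than the 12-month one.

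The unadjusted test is valid but inefficient. How much it loses depends on the unknown within-set correlation, and it matters mainly for effects smaller than 50%. The missing definition concerns the on-study rate only. It leaves room for a choice that could lean either way, and neither direction nor size can be fixed from the documents. The plan should be changed on these points, but nothing here shows that its test would produce a false positive.

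**What to change.** In section 4.1.2:

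- State one number of controls, reconcile it with section 4.1.1, and restate the power for that ratio with a 6-month SD.
- Make the primary analysis a regression of each person's on-study ALSFRS-R slope on group and pre-treatment rate, and report the group effect with its confidence interval.
- Compute slopes from the baseline, week 4 and monthly scores to month 6, leaving out the week 1 to 3 training scores. State the minimum number of those scores (for example four).
- Apply the same 6-month window and data-availability rules to controls.
- Add a mixed model on the same scores as a sensitivity analysis for dropout and death. Enter baseline once: using it both as a month 0 response and as a slope covariate gave 10 to 12% false positives in simulation when the groups started 3 points apart.

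The slope regression is preferred as primary because it is simpler and, in step 3, at least as powerful as the mixed model. Neither removes bias if dropout follows the unobserved true rate: simulated false positives were then 10/10/6% for slope regression and 8/10/7% for the mixed model, against 16/13/9% for the completer t-test. The sensitivity results should be read with that limit in mind. The cost is SAP wording and a little more analysis work, with no new patients or visits.

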### **3 DESIGN & PROCEDURES:**

#### **3.1 Design Overview**

This will be a 6-month, widely inclusive, largely remote/virtual, single-center, open-label pilot trial utilizing a historical control group. Following informed consent and screening, participants will take the intervention (see section 3.2.1) for 6-months. Treatment with the intervention Theracurmin HP and all study outcome measures and labs are being performed exclusively for research purposes. Collected data includes ALSFRS-R, fecal sample microbiome sampling, adverse events, and concomitant medications. Participants will be asked to register for an account on PLM with the help of the study coordinator. User IDs associated with their PLM account will be recorded by the study coordinator and shared with study staff at PLM. When registering, participants will have the opportunity to review PLM's terms and conditions (Appendix A) as well as their privacy policy (Appendix B). After the baseline video/telephone visit, participants will be asked to enter the following data: weight and height, Theracurmin treatment evaluations (Appendix C), ALSFRS-R score (Appendix D) and Thrive Questionnaires (Appendix E). Participants will be given the following study documents and materials shipped to their home:

A PLM bag (Appendix F) including:

1. Welcome letter (Appendix G)
2. Study One-Sheet (Appendix H)
3. Study drug
4. Microbiome kits
5. PatientsLikeMe gifts

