## **3.4 Study Schedule**

Following informed consent and screening, enrollment visit activities will commence and Therarcurmin treatment will be started. Treatment and all study activities will end at month 6. Participants will be required to make 4 video/telephone visits with the Duke study team (enrollment, weeks 1, 2, and 3). Participants will not be required to make any physical visits to Duke. At months 2-6, participants will make “Internet PLM visits” by measuring their own ALSFRS-R score and weight and height, and logging onto the PLM website to record it as well as perceived efficacy, perceived side effects, perceived compliance, changes in concomitant medications and Thrive questionnaires. Participants will be reminded to log into their PLM profile and record the above-mentioned data points via email and text reminders from PLM. The study coordinator will call/video participants at enrollment, weeks, 1, 2, 3 and for training and any time afterward when participants have not entered data for 2 weeks beyond expected entries. The call script for such communications can be found in Appendix I.

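### The 90% power target rests on a 12-month decline, a 12-month SD and 50 controls, but the trial lasts 6 months and Section 4.1.1 calls for three controls per participant

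*Combined protocol and SAP*

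**What the plan says.** Section 4.1.2 plans a t-test of the ALSFRS-R progression rate in participants against matched historical controls. Its sizing inputs are:

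- Decline: "The mean ALS-FRS progression in 12 months is 11 points", which it also gives as about 0.9 points per month.
- Spread: "the standard deviation at 12 months is ~8 ALS-FRS points".
- Effect: the mean rate is halved.
- Error rates: one-tailed 5%, power 90%.
- Attrition: "There will be a dropout rate of 15% over 6 months".

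The conclusion is that "we will again need to enroll 50 participants (and compare them to 50 matched historical controls").

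Elsewhere the plan describes a different comparison. On duration, Section 3.1 reads "This will be a 6-month, widely inclusive, largely remote/virtual, single-center, open-label pilot trial" and Section 3.4 reads "Treatment and all study activities will end at month 6". On controls, Section 4.1.1 reads "For each enrolled participant, three matched historical controls will be identified from the PatientsLikeMe database", which is 150 controls for 50 participants.

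**The concern.** Two features of the sizing do not match the planned test, and no section bridges the gap.

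**Time base.** Decline and SD are 12-month quantities; only attrition is given for 6 months. Converting the mean is easy, because Section 3.3.1 says the scale declines linearly over a wide range. Converting the SD is not, because the precision of an individual's rate depends on how long that person is followed. The plan gives no 6-month SD, no SD of the monthly rate and no conversion.

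**Control count.** Adjacent sections give 50 and 150 for the same primary comparison. If 150 are to be found but only 50 analysed, the plan has no rule for choosing the 50.

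This is the only power statement for this trial's primary test, so it is what a reader would use to interpret a null result. The controls come from an existing database and the trial is open-label. A control count left open could therefore be settled after control outcomes are visible.

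**Working it through.** **Method.** Two-sample t-test, noncentral-t power, one-sided 5%, equal SDs, controls treated as independent, no credit for matching. With n₁ participants and n₂ controls, the noncentrality is Δ / (SD × √(1/n₁ + 1/n₂)) on n₁ + n₂ − 2 degrees of freedom.

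**Step 1: the plan's own figure (12 months, 1:1).** Δ = 0.5 × 11 = 5.5 and SD = 8, so the standardised effect is 5.5/8 = 0.6875.

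- Per group for 90% power: 37. Enrolled: 37/0.85 = 43.5, i.e. 44.
- With the rounded rate, Δ = 0.5 × 0.9 × 12 = 5.4: 39 per group, and 39/0.85 = 45.9, i.e. 46.
- Enrolling 50 leaves 50 × 0.85 = 42.5, taken as 42 completers. Power for 42 v 42 is 93.0% (92.3% with Δ = 5.4).

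The stated 50 is therefore not the number these inputs yield, but it errs on the safe side.

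**Step 2: the same comparison at 6 months.** With linear decline, Δ = 0.5 × 11/2 = 2.75. The 6-month SD is not in the documents, so I assume a range:

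- 4.0: SD proportional to time (8/2). The standardised effect is again 2.75/4 = 0.6875.
- 4.8 and 5.25: intermediate values.
- 5.66: SD proportional to root time (8/√2), taken as an outer bound.

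The 1:3 column is 42 v 126 and the 1:1 column is 42 v 42, keeping only the controls matched to completers.

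| Assumed 6-month SD | Power, 1:3 | Power, 1:1 | Slowing detectable with 90% power, 1:3 | Same, 1:1 |
|---|---|---|---|---|
| 4.0 | 98.6% | 93% | 38% | 47% |
| 4.8 | 94% | 83% | 46% | 56% |
| 5.25 | 90% | 77% | 50% | 61% |
| 5.66 | 86% | 71% | 54% | 66% |

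Detectable slowing is the difference that gives 90% power divided by the 6-month control decline of 5.5. At SD 4.8, for example, it is 2.51/5.5 = 46% with 1:3 and 3.09/5.5 = 56% with 1:1. The planned effect is 50%.

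If the SD did not shrink at all (8, an extreme case), power would be 61% with 1:3 and 47% with 1:1.

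**Step 3: largest 6-month SD that still gives 90% power.**

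| Controls retained | 1:3 | 1:1 |
|---|---|---|
| Only those matched to completers (42 v 126; 42 v 42) | 5.25 | 4.27 |
| None lost (42 v 150; 42 v 50) | 5.36 | 4.46 |
| As the first row, with Δ = 2.7 (0.9 points per month) | 5.16 | 4.19 |

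Under each of these conventions, roughly one point of 6-month SD separates the two control counts.

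**The case against.** **The test compares rates, so duration cancels.** This is right for the mean. It is right for the standardised effect only if the SD halves exactly, which the plan does not claim.

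**The two mismatches offset.** Shorter follow-up can lower power, while three controls each raise it. Suppose, for illustration, that the 12-month SD of 8 describes a change between two scores, each with independent measurement noise of 3 points. The between-patient variance at 6 months is then (64 − 2 × 9)/4 = 11.5. A least-squares slope through seven monthly scores (months 0 to 6, sum of squared deviations 28) adds 36 × 9/28 = 11.6. The 6-month-equivalent SD is √23.1 = 4.8. With no noise it is 4.0. Power with three controls each is then 94% to 98.6%. This stands as a reason not to call the trial underpowered. On the same range, though, one control each gives 83% to 93%, so the control count still decides whether the target is met.

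**The two counts can be read together.** Section 4.1.2 might state a minimum and Section 4.1.1 how many controls will be sourced. That would be conservative, but the plan does not say so, nor which controls enter the test.

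**Historical controls need not be lost when a participant drops out.** This is fair. It moves the window only from 4.27–5.25 to 4.46–5.36.

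**The text may simply have been carried over.** Section 2.3 reads "We previously conducted an open-label, single-center, hybrid-virtual 12-month trial of Lunasin for patients with ALS". That trial had 50 participants and 90% power, and Section 4.1.2 says 50 are needed again. This is suggestive only: the earlier trial also used three controls per participant, and the attrition input here was written for 6 months.

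**Conclusion.** The point holds. The 90% target and the 50 v 50 statement are justified for a 12-month, 1:1 comparison, whereas the plan describes a 6-month trial with three controls per participant. Whether the trial has 90% power cannot be settled from the documents, because the 6-month SD is missing. With three controls each the target is met up to a 6-month SD of about 5.25; with one each, only up to about 4.3. Between those values the answer turns on a choice the plan leaves open.

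These cut-offs assume linear decline, 42 completers, equal SDs, independent controls and no gain from matching. A slope that also used dropouts' partial scores could add some power. The textual mismatch is certain; the power figures depend on the assumed SDs. The plan should be corrected, but the fault is not fatal to the design.

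**What to change.** Keep 50 participants and revise Section 4.1.2 as follows:

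1. Replace the 50 controls with three per participant, in agreement with Section 4.1.1. State that all three enter the primary comparison, and fix this before control outcomes are examined.
2. Compute the progression rate in the same way in both groups, for example as a least-squares slope over the monthly scores to month 6, so that the SD used for sizing belongs to the quantity tested.
3. Take the SD of that 6-month rate from the PatientsLikeMe data, which already supplied the 12-month figures, and cite it in place of the 12-month SD.
4. Restate the power, or the smallest slowing detectable with 90% power, for the 6-month, 1:3 comparison.

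The cost is a change of wording and one summary from an existing database, assumed obtainable from the same source. No participants or procedures are added. The drawback is that the restated power may be below 90%.
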